4.4 SURGICAL PROCEDURES

4.4.1 PRECAUTIONS FOR PHOTSENSITIVITY DURING SURGERY

During surgery, light-opaque drapes will be used to cover all skin, including the area around the surgical site. The patient's eye lids will be closed with tape and covered with goggles that block the appropriate light wavelengths that might damage the retina. The patient will receive instructions on how to prevent exposure to sunlight and bright indoor lighting for a period of 24 hours post surgery (see Appendix I: Section 12).

4.4.2 SURGICAL TREATMENT

During surgery, the intraoperative fluorescence observations and PpIX concentration measurements will be taken by the surgeon and recorded by research personnel. The surgical site will be illuminated with UV/blue light in the wavelength range of 350-490nm with an irradiance of 20-40 mWcm⁻². A fluorescence image will be taken using a commercially available operating room microscope. A white-light image will also be taken using the same microscope in non-fluorescence mode. Each tissue biopsy will be taken at the discretion of the operating surgeon (the biopsy location on the fluorescence image will be recorded) and divided in 3 parts that will be analyzed by histopathology, fluorometry, and fluorescence microscopy. At each site, the position of the biopsy in the tumor bed will be determined by frameless stereotaxy using an Optical Tracking System (OTS) for correlation with pre- and post-operative CT and/or MRI scans. Biopsies of 50mg or less are taken with biopsy forceps .

4.4.3 INTRA-OPERATIVE MEASUREMENTS

The procedures for performing fluorescence imaging and spectroscopy during and following resection are well established from our prior experience.

4.4.3.1 BULK TUMOR MEASUREMENTS

1. Under white light illumination, the surgeon will identify biopsy sites of tumor and normal tissue with a probe and corresponding white-light and fluorescence images will be taken.
2. A biopsy will be taken of each of the sites identified under white light illumination and under fluorescence imaging.

Additionally, the location of the biopsies will be determined with an Optical Tracking System for post-operative correlation with pre- and post-operative CT and/or MR-scans.

The exact step-by step operating room procedures for these intra-operative measurements are described in Appendix III, Section 12.

4.4.4 SPECIMEN HANDLING

Each biopsy will be divided immediately by the pathologist using a scalpel into 3 parts: 1 will be placed in formalin for standard histopathological assessment. The other 2 parts will be protected from light exposure, snap frozen in liquid nitrogen and will be kept at -80 °C in a light protected environment until further use, that is analysis by spectrofluorimetry and confocal fluorescence microscopy (see below for procedures).

The intra-operative fluorescence imaging information will not be used in this trial to modify or extend the surgical resection.

4.5 TISSUE AND DATA ANALYSIS

4.5.1 TISSUE ANALYSIS

Each single biopsy, taken for the purposes of this single-center study, is divided in 3 parts to perform 3 different types of analyses. All of these tissue samples will be analyzed according to standard operating procedures for each analysis. . These biopsies will not be used as part of patient care.

Note: In case a biopsy is too small to be divided in three parts, the biopsy will be fixed in formalin and given to [name] for histopathological analysis only.

4.5.1.1 1ST PART OF BIOPSY: HISTOPATHOLOGICAL ANALYSIS

The first part of each biopsy will be fixed in formalin and given to [name] who will prepare standard Hematoxylin & Eosin (H&E) stained sections. This histopathology will be assessed by a single experienced neuropathologist, [name]. Grading and assessment of tumor extent will be determined in the usual fashion.

4.5.1.2 2ND PART OF BIOPSY: PpIX QUANTIFICATION

The second part of each biopsy will be protected from light exposure, immediately snap-frozen in liquid nitrogen, and stored at -80 °C before being sent to [name] laboratory at the University Health Network Hospital in Toronto. The PpIX concentration of that sample will be determined using a procedure developed by Lilge *et al.* [19] which, briefly, is as follows: After thawing, the tissue will first be finely chopped with a scalpel blade, and suspended by placing it in Solvable™ (Dupont, Boston) at 50 °C in a water bath and shaken for 1 hour, then mechanically homogenized and re-incubated in Solvable for another hour. The fluorescence of aliquots of the suspended sample will then be measured in a scanning spectrofluorimeter (PTI, London, ON, Canada). The PpIX concentration will then be determined by spiking the sample with known concentrations of PpIX. This procedure is currently used as the standard technique in the same

investigator-group's NIH-sponsored, multi-center, Photofrin-mediated PDT brain tumor clinical trial. For 100 mg brain tissue samples, it has a lower detection limit of 0.02µg PpIX per gram of tissue. The anticipated concentration range in tumor for the lowest ALA dose is expected to be 100 times this value.

4.5.1.3 3RD PART OF BIOPSY: (CONFOCAL) FLUORESCENCE MICROSCOPY

The third part of each biopsy will be protected from light exposure and immediately snap-frozen in liquid nitrogen. It will then be light protected and stored at -80 °C in [name] lab in Toronto. (Confocal) fluorescence microscopy will be used to determine the microdistribution of PpIX. This technique is also in routine use in [name] laboratory [17]. Briefly, serial 5µm frozen sections of each biopsy will be made. Alternate sections will be stained for standard histological comparison with the H&E sections above. The quality of H&E sections made in this way is not adequate for clinical diagnosis, but does allow direct one-to-one identification of areas of tumor involvement when compared with the confocal fluorescence microscopy of the adjacent sections. The fluorescence images will be obtained using a UV/visible Zeiss (Thornwood, NY) 510 confocal fluorescence microscope equipped with multiple detection wavelength channels. Regions of tumor and normal brain tissue will be identified and the relative fluorescence intensity and heterogeneity of the fluorescence will be quantified.

4.6 POST OPERATIVE ACTIVITIES

4.6.1 POST OPERATIVE BLOOD SAMPLE COLLECTION

Blood will be drawn for liver function tests 48 hours post tumor resection. If abnormal (\geq than Grade 3), weekly liver function tests will be drawn for 2 weeks. They will then be monitored on a monthly basis until they normalize (see Section 4.7.3). Subsequent to study completion, patients will have regular surveillance as per the current standard of care.

4.7 REPORTING ADVERSE EVENTS ASSOCIATED WITH SYSTEMIC ALA

There have been over 19 published reports of systemic administration of ALA for PDT in at least 230 patients [14, 15, 20-40] with ALA doses up to 60 mg/kg. No serious adverse events or reactions have been reported; however, skin photosensitivity, nausea and vomiting, liver function abnormalities and some other events (as outlined below have been temporally related to ALA administration).

4.7.1 SKIN PHOTSENSITIVITY

Since ALA-induced PpIX accumulation occurs mostly in cells of epithelial origin, accumulation in skin and subsequent cutaneous injury after sun exposure has been reported. Four volunteers, who ingested doses of ALA ranging from 12.5 to 35 mg/kg, developed photosensitization of skin (but no sunburns) that persisted for approximately 24 hours [37], and a severe sunburn occurred 8 hours after a 10 mg/kg load in a volunteer who was exposed to bright light [38]. The reactions reported in clinical PDT trials (30-60

mg/kg) were usually mild, consisted mainly of erythema or a “mild photosensitivity reaction” and resolved within 24 to 48 hours. Blister formation and skin necrosis has not been reported [40]. Ocular sensitivity has not been reported with systemic ALA.

Based on this evidence, the patients in our study will receive written and verbal instructions regarding skin exposure to ambient light (see Appendix I). They will be advised to stay indoors for 1 day (24 hours), cover exposed parts of their bodies, and protect their eyes from direct sun rays, strong fluorescent or incandescent lighting (e.g. a dentist's lamp or examining light) or strong residential direct indoor lighting (e.g. direct sunlight through a window for more than a few minutes, direct spotlights, floodlights, etc.) for this period. After 1 day, they may expose a small area of skin to the sun for 15 minutes to test for residual sun sensitivity. There is no proof that sun screens are of any value.

4.7.2 NAUSEA AND VOMITING

Dose-dependent mild nausea and occasional vomiting have been reported. Nausea was seen during the administration of hourly fractionated doses [21,30,31,34] or immediately after bolus administration [24,29,37] (i.e., in approximately 2/3 of patients given 60 mg/kg and 1/3 of patients given 30 mg/kg). Vomiting occurred about 12 hours later in a few cases and resolved by 24 hours. The patients in this study will be evaluated and treated as indicated by the severity of their symptoms.

4.7.3 LIVER FUNCTION TEST ABNORMALITIES

Dose-dependent abnormalities in liver function tests have also been reported. The most common abnormality was a rise in transaminases, usually AST [24,25,26,29,31,35,37]. In two studies up to 2/3 of patients given 60 mg/kg and 1/5 of those given 30 mg/kg had elevated AST levels [21,30]. This rise was small in most other reports, but in these two studies (possibly describing the same series of patients), 3 patients had levels 3 to 5 times above normal. In all studies but one, the abnormalities resolved 72 hours later: 5 of 18 patients' transaminases normalized in 10 days and one patient with a history of excessive alcohol intake had elevated levels at 30 days [34]. Only nine patients in these studies had transient elevations in bilirubin (less than two times normal). No study correlated the liver function test abnormalities with the occurrence of nausea and vomiting in individual patients. Based on this experience, follow-up in our patients will consist of testing of liver function tests at 48 hours post tumor resection and, if \geq than Grade 3, weekly for 2 weeks and then at monthly intervals thereafter to resolution.

4.7.4 OTHER EVENTS

One patient developed a lichenoid reaction a week after oral ALA (60 mg/kg) which resolved after 3 weeks [34]. No abnormalities have been noted in serum electrolytes or hematologic indices.

4.8 ADVERSE EVENT REPORTING

Patients will be monitored postoperatively for adverse events until 30 days after the study drug administration. Adverse events will be graded using the NCI CTC 3.0 criteria. In the

case of any of the events described above, the patient will be examined by a study physician and appropriate medical action taken. The event will be recorded in the patient's study file with the date of occurrence, date of resolution, severity and the actions taken. Any unexpected or serious adverse events, Grade 3 or above, or drug reaction beyond the scope of what was described above, will be reported on a MedWatch form to the Principal Investigator, the Case Comprehensive Cancer Center Clinical Trial Regulatory Affairs Office, Institutional Review Board, Case Comprehensive Cancer Center Data Safety and Toxicity Committee, Food and Drug Administration, DUSA Pharmaceuticals via [name].

FDA Reporting

The University Hospitals Cleveland Medical Center Principal Investigator, as holder of the IND, will be responsible for all communication with the FDA. In accordance with 21 CFR 312.32, the University Hospitals Cleveland Medical Center Principal Investigator is responsible for notifying the FDA of SAEs that are serious, unexpected (not listed in the Investigator Brochure or package insert) and judged to be related (i.e., possible, probable, definite) to the study drug. Events meeting the following criteria need to be submitted to the FDA as Expedited IND Safety Reports.

7 Calendar Day IND Safety Report

Any unexpected fatal or life-threatening suspected adverse event represent especially important safety information and, therefore, must be reported more rapidly to FDA (21 CFR 312.32(c)(2)). Any unexpected fatal or life-threatening suspected adverse event must be reported to FDA no later than 7 calendar days after the University Hospitals Cleveland Medical Center/ Principal Investigator initial receipt of the information (21 CFR 312.32(c)(2)). University Hospitals Cleveland Medical Center Principal Investigator will complete a Medwatch Form FDA 3500A and notify the FDA by telephone or facsimile transmission.

15 Calendar Day IND Safety Report

The timeframe for submitting an IND safety report to FDA and all participating investigators is no later than 15 calendar days after the University Hospitals Cleveland Medical Center Principal Investigator determines that the suspected adverse event or other information qualifies for reporting (21 CFR 312.32(c)(1)). This includes any serious, unexpected adverse events considered reasonably or possibly related to the investigational agent. University Hospitals Cleveland Medical Center Principal Investigator will complete a Medwatch Form FDA 3500A and notify the FDA by telephone or facsimile transmission. If FDA requests any additional data or information, the /University Hospitals Cleveland Medical Center Principal Investigator must submit it to FDA as soon as possible, but no later than 15 calendar days after receiving the request (21 CFR 312.32(c)(1)(v)).

Follow-up IND Safety Report

Any relevant additional information that the University Hospitals Cleveland Medical Center Principal Investigator obtains that pertains to a previously submitted IND safety report must be submitted to FDA as a Follow-up IND Safety Report without delay, as soon as the information is available (21 CFR 312.32(d)(2)). The University Hospitals

Cleveland Medical Center Principal Investigator will maintain records of its efforts to obtain additional information.

Reporting Serious Problems to FDA

Medwatch Form FDA 3500A:

<http://www.fda.gov/Safety/MedWatch/HowToReport/DownloadForms/default.htm>

[contact]

Fax: [name]

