4.0 RESEARCH DESIGN

4.1 SUMMARY OF TRIAL DESIGN

Summary of Trial Design: This study will enroll evaluable patients undergoing surgical resection of malignant, grade IV gliomas in both of two groups: those with newly diagnosed GBM and those with recurrent GBM. Patient, in each group (primary vs recurrent GBM) will be randomized to one of 2 levels of ALA dose (10 and 20 mg/kg) to be given orally at 3 hours prior to anticipated midpoint of surgery.

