4.2 RANDOMIZATION

Patients who have consented to this protocol will be randomly assigned to one of two ALA dose groups (Table 3). Randomization will be stratified by whether the tumor is newly diagnosed (i.e. *de novo*) or recurrent. The data center will prepare sealed, opaque envelopes with the randomized assignment to ALA dose and administration time and notify the pharmacy of the trial site so that so that the correct ALA dose can be prepared.

Neurosurgeons and investigators responsible for determining pathologic characteristics, for quantifying fluorescence images, for extracting chemical PpIX, for co-localizing fluorescence images with MR images will be blinded to the ALA dose and administration time. In case of emergency, such as toxicity or allergic reaction attributable to the drug, the research pharmacist on call will break the blind and inform the PI and the physician responsible for clinical management.

A safety monitoring board has been developed at the Case Comprehensive Cancer Center at Case Western Reserve University. Also, forms will be filled out by the surgeon postoperatively on a daily basis, the patient's surgeon will report any adverse effects. In addition to specific signs and symptoms, liver function tests will be ascertained at 48

hours and, if abnormal, these tests will be continued on a twice-weekly basis until they peak and then at weekly intervals thereafter to resolution. In the case of any adverse event, the patient will be examined by the study physician and appropriate medical action taken.

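### Adverse-event collection is stated to begin after surgery, so the hours from ALA ingestion to the end of the operation, when immediate nausea is expected, have no scheduled collection

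*Combined protocol and SAP*

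**What the plan says.** The window is defined in section 4.8: "Patients will be monitored postoperatively for adverse events until 30 days after the study drug administration". Section 4.2 describes the only scheduled instrument: "forms will be filled out by the surgeon postoperatively on a daily basis, the patient's surgeon will report any adverse effects".

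The timing of the drug is in section 4.1, where ALA is "to be given orally at 3 hours prior to anticipated midpoint of surgery".

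The expected early events are in section 4.7.2. It states: "Dose-dependent mild nausea and occasional vomiting have been reported". For a bolus, nausea was seen "immediately after bolus administration [24,29,37] (i.e., in approximately 2/3 of patients given 60 mg/kg and 1/3 of patients given 30 mg/kg". On vomiting it says: "Vomiting occurred about 12 hours later in a few cases and resolved by 24 hours".

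Three further provisions bear on the point, and none carries a start time:

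- Section 4.7.2 on nausea and vomiting: "The patients in this study will be evaluated and treated as indicated by the severity of their symptoms".
- Section 4.8, just after the window sentence, has a study physician examine any patient with one of the events listed in 4.7. The event is then entered in the study file with its dates, severity and actions.
- Section 4.2 requires examination for any adverse event and gives an emergency unblinding route for toxicity or allergic reaction.

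**The concern.** The two ends of the window hang on different events. The end is counted from the dose and the start from the operation. Because the dose comes first, the hours between ingestion and the end of surgery lie outside the stated monitoring. Those are the hours in which the protocol's own summary of experience places nausea after a bolus.

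At stake is the quality of the safety description in a trial that randomizes dose. An event described as dose-dependent should be looked for in the same way in every patient from the moment of dosing. Nausea first asked about after a craniotomy under anesthesia is hard to attribute to the drug. A record taken before anesthesia would not have that problem.

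**Working it through.** The plan states no figure for this interval, so there is none to reproduce. The check is one of timing.

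1. **Length of the interval.** Input: dose 3 h before the anticipated midpoint (4.1). Let D be the duration of surgery, which the documents do not give. If the schedule is kept, ingestion to end of surgery is 3 + D/2 hours. For assumed D = 3, 4 and 6 h this is 4.5, 5.0 and 6.0 h. It exceeds 3 h for any D.

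2. **The part before surgery starts.** This is 3 − D/2 hours: 1.5 h at D = 3, 1.0 h at D = 4 and 0 h at D = 6, less any induction time. The period in which a patient can report a symptom free of anesthesia is therefore short, about 1.5 h at most under these durations. At D = 6 the planned dose coincides with the start of surgery, so 6 h marks the edge of the range.

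3. **Which named events fall in the interval.**
   - Nausea immediately after a bolus (4.7.2): inside. Section 7.1.2 describes a drink of under 60 ml and mentions no fractionation, so the bolus pattern is the relevant one.
   - Vomiting at about 12 h (4.7.2): outside whenever 3 + D/2 < 12, that is, for any operation shorter than 18 h.
   - Skin reaction: the one case with a timed onset in 4.7.1 came at 8 h, beyond the 4.5 to 6 h above.
   - Liver tests at 48 h after resection (4.6.1): outside.

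   Nausea is thus the one listed event whose cited onset lies in the interval.

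4. **What would be kept about an early event that is noticed.** Section 4.8 asks for the date of occurrence, not the clock time. Dose and surgery would normally share a date, so such a record may not show whether onset came before or after anesthesia. The patient data set in 6.1 has 11 items; none is an adverse event or the time of ingestion.

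5. **How many patients.** The documents cannot settle this. Rates are cited only for 30 mg/kg (about 1/3) and 60 mg/kg (about 2/3).
   - As an illustration, assume the rate is proportional to dose. Then 1/3 × 10/30 = 1/9 and 1/3 × 20/30 = 2/9. With 60 patients per dose (30 + 30, Table 3 of section 4.4.3), that is 60/9 ≈ 7 and 120/9 ≈ 13 with nausea.
   - The range runs from 0 to 20 per dose; 20 applies if the 30 mg/kg rate held at both doses.
   - These are patients with nausea at any time, not patients lost to the record. How many would go unrecorded is unknown.

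6. **Would full capture support a dose comparison?** Under the same assumption, the pooled standard error is √(2 × 0.167 × 0.833/60) = 0.0680. The unpooled one is √((0.0988 + 0.1728)/60) = 0.0673. Then z = (0.111 − 1.96 × 0.0680)/0.0673 ≈ −0.33, a power of about 37% at two-sided 0.05. The interest is descriptive.

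**The case against.** The strongest reply is that nothing forbids recording an early event. The duty to record in 4.8 covers the nausea of 4.7.2 and has no start time. Section 4.2 calls for examination in any adverse event, and its emergency route is not confined to the postoperative period. A form completed after surgery can also note an earlier onset. This stands, and it rules out saying that early events are missed. It does not close the gap. Those provisions act once somebody has noticed an event; none has anyone look for one before the end of surgery, and the sentence that opens 4.8 defines monitoring as postoperative.

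It is also fair to say that the nausea is described as mild, that the cited rates come from higher doses, and that safety is not among the primary, secondary or tertiary objectives. All of this limits the consequence.

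A reader might infer more from the gap, without support in the documents:

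- **That a vomited dose would distort the accuracy results.** Section 4.7.2 puts vomiting at about 12 hours, well after the biopsies. The direction would be unknown in any case: six of the 12 scenarios in Table 1 of section 8.2 give 10 mg/kg the higher Youden index, for example 0.55 against 0.45.
- **That the trial would understate a safety difference between doses.** No such comparison is planned, and the illustration above gives it little power.
- **That allergic reactions would be lost.** The documents give no timing for them, and section 4.2 provides for them as emergencies.

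**Conclusion.** The point holds in a limited form. The stated window and the only scheduled form both begin after the period in which the protocol expects one of its named events. Events between ingestion and the end of surgery are not systematically collected. They may be under-recorded, or recorded in a way that cannot separate them from anesthesia and surgery.

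The length of the gap follows from section 4.1 if the schedule is kept; only the operating time is assumed. The number of patients affected cannot be stated, because no nausea rate is given for 10 or 20 mg/kg. The primary analysis and the sample size are unaffected. The change is worth making because it corrects a stated rule at little cost. A few parts of the file, among them 4.3.2, 7.2, Appendix I and the flow chart of Appendix III, were not available for this check.

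**What to change.** Three changes:

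1. In section 4.8, let adverse-event collection run from ALA ingestion until 30 days after study drug administration, so that both ends are counted from the dose.
2. Add to the form in section 4.2 one entry for the preoperative and intraoperative period, with the clock time of ingestion and of onset of any event.
3. Reconcile sections 4.2, 4.7.2 and 4.8 so that all three give the same starting point.

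The cost is slightly more data entry before surgery and a somewhat higher reported event rate. Someone must be assigned to the entry before the operation. The section on surgical treatment (4.4.2) has research personnel recording during surgery, but it does not place them with the patient at ingestion. Section 7.1.2 already has the pharmacist and the surgeon or a delegate weigh the drug before use. The change concerns data collection only and alters no dose, schedule or rule of clinical care.
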